**Appendix 11: C-SSRS since Last Visit (cont.)**

SUICIDAL BEHAVIOR (Check all that apply, so long as these are separate events; must ask about all types)	Since Last Visit

Actual Attempt: A potentially self-injurious act committed with at least some wish to die, as a result of act. Behavior was in part thought of as method to kill oneself. Intent does not have to be 100%. If there is any intent/desire to die associated with the act, then it can be considered an actual suicide attempt. There does not have to be any injury or harm, just the potential for injury or harm. If person pulls trigger while gun is in mouth but gun is broken so no injury results, this is considered an attempt. Inferring intent: Even if an individual denies intent/wish to die, it may be inferred clinically from the behavior or circumstances. For example, a highly lethal act that is clearly not an accident so no other intent but suicide can be inferred (e.g., gunshot to head, jumping from window of a high floor/story). Also, if someone denies intent to die, but they thought that what they did could be lethal, intent may be inferred. Have you made a suicide attempt? Have you done anything to harm yourself? Have you done anything dangerous where you could have died? What did you do? Did you _____ as a way to end your life? Did you want to die (even a little) when you _____? Were you trying to end your life when you _____? Or did you think it was possible you could have died from _____? Or did you do it purely for other reasons / without ANY intention of killing yourself (like to relieve stress, feel better, get sympathy, or get something else to happen)? (Self-Injurious Behavior without suicidal intent) If yes, describe.
	
Yes No  
 
Total # of Attempts _____
 
Yes No  


Has subject engaged in Non-Suicidal Self-Injurious Behavior?
 
Interrupted Attempt: When the person is interrupted (by an outside circumstance) from starting the potentially self-injurious act (if not for that, actual attempt would have occurred). Overdose: Person has pills in hand but is stopped from ingesting. Once they ingest any pills, this becomes an attempt rather than an interrupted attempt. Shooting: Person has gun pointed toward self, gun is taken away by someone else, or is somehow prevented from pulling trigger. Once they pull the trigger, even if the gun fails to fire, it is an attempt. Jumping: Person is poised to jump, is grabbed and taken down from ledge. Hanging: Person has noose around neck but has not yet started to hang - is stopped from doing so. Has there been a time when you started to do something to end your life but someone or something stopped you before you actually did anything? If yes, describe.
	
Yes No  
 
Total # of interrupted _____

Aborted Attempt: When person begins to take steps toward making a suicide attempt, but stops themselves before they actually have engaged in any self-destructive behavior. Examples are similar to interrupted attempts, except that the individual stops him/herself, instead of being stopped by something else. Has there been a time when you started to do something to try to end your life but you stopped yourself before you actually did anything? If yes, describe.
	
Yes No  
 
Total # of aborted _____

Preparatory Acts or Behavior: Acts or preparation towards imminently making a suicide attempt. This can include anything beyond a verbalization or thought, such as assembling a specific method (e.g., buying pills, purchasing a gun) or preparing for one's death by suicide (e.g., giving things away, writing a suicide note). Have you taken any steps towards making a suicide attempt or preparing to kill yourself (such as collecting pills, getting a gun, giving valuables away or writing a suicide note)? If yes, describe.
	
Yes No  

Suicidal Behavior: Suicidal behavior was present during the assessment period?
	
Yes No  


Suicide:
	
Yes No  

Answer for Actual Attempts Only
	
Most Lethal Attempt Date:

Actual Lethality/Medical Damage: 0. No physical damage or very minor physical damage (e.g., surface scratches). 1. Minor physical damage (e.g., lethargic speech; first-degree burns; mild bleeding; sprains). 2. Moderate physical damage; medical attention needed (e.g., conscious but sleepy, somewhat responsive; second-degree burns; bleeding of major vessel). 3. Moderately severe physical damage; medical hospitalization and likely intensive care required (e.g., comatose with reflexes intact; third-degree burns less than 20% of body; extensive blood loss but can recover; major fractures). 4. Severe physical damage; medical hospitalization with intensive care required (e.g., comatose without reflexes; third-degree burns over 20% of body; extensive blood loss with unstable vital signs; major damage to a vital area). 5. Death
	
Enter Code _____

Potential Lethality: Only Answer if Actual Lethality=0 Likely lethality of actual attempt if no medical damage (the following examples, while having no actual medical damage, had potential for very serious lethality: put gun in mouth and pulled the trigger but gun fails to fire so no medical damage; laying on train tracks with oncoming train but pulled away before run over). 0 = Behavior not likely to result in injury 1 = Behavior likely to result in injury but not likely to cause death 2 = Behavior likely to result in death despite available medical care
	
Enter Code _____

The actual forms will be provided to the sites and should be used for assessment.

## Appendix 12 C-SSRS Already Enrolled Subjects

# COLUMBIA-SUICIDE SEVERITY RATING SCALE (C-SSRS)

Already Enrolled Subjects

Version 1/14/09

*Posner, K.; Brent, D.; Lucas, C.; Gould, M.; Stanley, B.; Brown, G.; Fisher, P.; Zelazny, J.;  
Burke, A.; Oquendo, M.; Mann, J.*

*Disclaimer:*

*This scale is intended to be used by individuals who have received training in its administration. The questions contained in the Columbia-Suicide Severity Rating Scale are suggested probes. Ultimately, the determination of the presence of suicidal ideation or behavior depends on the judgment of the individual administering the scale.*

*Definitions of behavioral suicidal events in this scale are based on those used in The Columbia Suicide History Form, developed by [name] and [name], Conte Center for the Neuroscience of Mental Disorders (CCNMD), New York State Psychiatric Institute, [name]. (Oquendo M. A., Halberstam B. & Mann J. J., Risk factors for suicidal behavior: utility and limitations of research instruments. In M.B. First [Ed.] Standardized Evaluation in Clinical Practice, pp. 103 -130, 2003.)*

*For reprints of the C-SSRS contact [name]., New York State Psychiatric Institute, [name]; inquiries and training requirements contact [[contact]](mailto:[contact])  
© 2008 The Research Foundation for Mental Hygiene, Inc.*

## Appendix 12: C-SSRS Already Enrolled Subjects (cont.)

SUICIDAL IDEATION		

Ask questions 1 and 2. If both are negative, proceed to "Suicidal Behavior" section. If the answer to question 2 is "yes", ask questions 3, 4 and 5. If the answer to question 1 and/or 2 is "yes", complete "Intensity of Ideation" section below.
	
Prior to Study Entry: Time He/She Felt Most Suicidal
	
Since Study Start:

1. Wish to be Dead Subject endorses thoughts about a wish to be dead or not alive anymore, or wish to fall asleep and not wake up. Have you wished you were dead or wished you could go to sleep and not wake up?
 
If yes, describe:
	
Yes No  
	
Yes No  

2. Non-Specific Active Suicidal Thoughts General non-specific thoughts of wanting to end one's life/commit suicide (e.g., "I've thought about killing myself") without thoughts of ways to kill oneself/as committed methods, intent, or plan during the assessment period. Have you actually had any thoughts of killing yourself?
 
If yes, describe:
	
Yes No  
	
Yes No  

3. Active Suicidal Ideation with Any Methods (Not Plan) without Intent to Act Subject endorses thoughts of suicide and has thought of at least one method during the assessment period. This is different than a specific plan with time, place or method details worked out (e.g., thought of method to kill self but not a specific plan). Includes person who would say, "I thought about taking an overdose but I never made a specific plan as to when, where or how I would actually do it...and I would never go through with it." Have you been thinking about how you might do this?
 
If yes, describe:
	
Yes No  
	
Yes No  


4. Active Suicidal Ideation with Some Intent to Act, without Specific Plan Active suicidal thoughts of killing oneself and subject reports having some intent to act on such thoughts, as opposed to "I have the thoughts but I definitely will not do anything about them." Have you had these thoughts and had some intention of acting on them?
 
If yes, describe:
	
Yes No  
	
Yes No  

5. Active Suicidal Ideation with Specific Plan and Intent Thoughts of killing oneself with details of plan fully or partially worked out and subject has some intent to carry it out. Have you started to work out or worked out the details of how to kill yourself? Do you intend to carry out this plan?
 
If yes, describe:
	
Yes No  
	
Yes No  

INTENSITY OF IDEATION		

The following features should be rated with respect to the most severe type of ideation (i.e., 1-3 from above, with 1 being the least severe and 3 being the most severe). For prior to study entry, ask about time he/she was feeling the most suicidal.
 
Prior to Study Entry - Most Severe Ideation: _____ Type # (1-3) Description of Ideation
 
Since Study Start - Most Severe Ideation: _____ Type # (1-3) Description of Ideation
	
Most Severe
	
Most Severe

Frequency How many times have you had these thoughts? (1) Less than once a week (2) Once a week (3) 2-3 times in week (4) Daily or almost daily (5) Many times each day
	
—
	
—

Duration When you have the thoughts how long do they last? (1) Fleeting - few seconds or minutes (4) 4-8 hours/most of day (2) Less than 1 hour/some of the time (5) More than 8 hours/persistent or continuous (3) 1-4 hours/a lot of time
	
—
	
—

Controllability Could/can you stop thinking about killing yourself or wanting to die if you want to? (1) Easily able to control thoughts (4) Can control thoughts with a lot of difficulty (2) Can control thoughts with little difficulty (5) Unable to control thoughts (3) Can control thoughts with some difficulty (6) Does not attempt to control thoughts
	
—
	
—


Deterrents Are there things - anyone or anything (e.g., family, religion, pain of death) - that stopped you from wanting to die or acting on thoughts of committing suicide? (1) Deterrents definitely stopped you from attempting suicide (4) Deterrents most likely did not stop you (2) Deterrents probably stopped you (5) Deterrents definitely did not stop you (3) Uncertain that deterrents stopped you (6) Does not apply
	
—
	
—

Reasons for Ideation What sort of reasons did you have for thinking about wanting to die or killing yourself? Was it to end the pain or stop the way you were feeling (in other words you couldn't go on living with this pain or how you were feeling) or was it to get attention, revenge or a reaction from others? Or both? (1) Completely to get attention, revenge or a reaction from others (4) Mostly to end or stop the pain (you couldn't go on living with the pain or how you were feeling) (2) Mostly to get attention, revenge or a reaction from others (5) Completely to end or stop the pain (you couldn't go on living with the pain or how you were feeling) (3) Equally to get attention, revenge or a reaction from others and to end/stop the pain (6) Does not apply
	
—
	
—

Version 1/14/09

**Appendix 12: C-SSRS Already Enrolled Subjects (cont.)**

SUICIDAL BEHAVIOR (Check all that apply, so long as these are separate events; must ask about all types)		Prior to Study Entry	Since Study Start
Actual Attempt: A potentially self-injurious act committed with at least some wish to die, as a result of act. Behavior was in part thought of as method to kill oneself. Intent does not have to be 100%. If there is ANY intent/desire to die associated with the act, then it can be considered an actual suicide attempt. There does not have to be any injury or harm , just the potential for injury or harm. If person pulls trigger while gun is in mouth but gun is broken so no injury results, this is considered an attempt. Inferring intent: Even if an individual denies intent/wish to die, it may be inferred clinically from the behavior or circumstances. For example, a highly lethal act that is clearly not an accident so no other intent but suicide can be inferred (e.g., gunshot to head, jumping from window of a high floor/story). Also, if someone denies intent to die, but they thought that what they did could be lethal, intent may be inferred. Have you made a suicide attempt? Have you done anything to harm yourself? Have you done anything dangerous where you could have died? What did you do? Did you _____ as a way to end your life? Did you want to die (even a little) when you _____? Were you trying to end your life when you _____? Or Did you think it was possible you could have died from _____? Or did you do it purely for other reasons / without ANY intention of killing yourself (like to relieve stress, feel better, get sympathy, or get something else to happen)? (Self-Injurious Behavior without suicidal intent) If yes, describe:		Yes No    Total # of Attempts _____  Yes No  	Yes No    Total # of Attempts _____  Yes No  
Has subject engaged in Non-Suicidal Self-Injurious Behavior? Interrupted Attempt: When the person is interrupted (by an outside circumstance) from starting the potentially self-injurious act (if not for that, actual attempt would have occurred). Overdose: Person has pills in hand but is stopped from ingesting. Once they ingest any pills, this becomes an attempt rather than an interrupted attempt. Shooting: Person has gun pointed toward self, gun is taken away by someone else, or is somehow prevented from pulling trigger. Once they pull the trigger, even if the gun fails to fire, it is an attempt. Jumping: Person is poised to jump, is grabbed and taken down from ledge. Hanging: Person has noose around neck but has not yet started to hang - is stopped from doing so. Has there been a time when you started to do something to end your life but someone or something stopped you before you actually did anything? If yes, describe:		Yes No    Total # of interrupted _____	Yes No    Total # of interrupted _____
Aborted Attempt: When person begins to take steps toward making a suicide attempt, but stops themselves before they actually have engaged in any self-destructive behavior. Examples are similar to interrupted attempts, except that the individual stops him/herself, instead of being stopped by something else. Has there been a time when you started to do something to try to end your life but you stopped yourself before you actually did anything? If yes, describe:		Yes No    Total # of aborted _____	Yes No    Total # of aborted _____
Preparatory Acts or Behavior: Acts or preparation towards imminently making a suicide attempt. This can include anything beyond a verbalization or thought, such as assembling a specific method (e.g., buying pills, purchasing a gun) or preparing for one's death by suicide (e.g., giving things away, writing a suicide note). Have you taken any steps towards making a suicide attempt or preparing to kill yourself (such as collecting pills, getting a gun, giving valuables away or writing a suicide note)? If yes, describe:		Yes No  	Yes No  
Suicidal Behavior: Suicidal behavior was present during the assessment period?		Yes No  	Yes No  
Completed Suicide:		Yes No  	Yes No  
Answer for Actual Attempts Only		Most Recent Attempt Date:	Most Lethal Attempt Date:
Actual Lethality/Medical Damage: 0. No physical damage or very minor physical damage (e.g., surface scratches). 1. Minor physical damage (e.g., lethargic speech; first-degree burns; mild bleeding; sprains). 2. Moderate physical damage, medical attention needed (e.g., conscious but sleepy, somewhat responsive; second-degree burns; bleeding of major vessel). 3. Moderately severe physical damage; medical hospitalization and likely intensive care required (e.g., comatose with reflexes intact; third-degree burns less than 20% of body; extensive blood loss but can recover; major fractures). 4. Severe physical damage; medical/hospitalization with intensive care required (e.g., comatose without reflexes; third-degree burns over 20% of body; extensive blood loss with unstable vital signs; major damage to a vital area). 5. Death		Enter Code	Enter Code
Potential Lethality: Only Answer if Actual Lethality=0 Likely lethality of actual attempt if no medical damage (the following examples, while having no actual medical damage, had potential for very serious lethality: put gun in mouth and pulled the trigger but gun fails to fire so no medical damage; lying on train tracks with oncoming train but pulled away before run over).  0 = Behavior not likely to result in injury 1 = Behavior likely to result in injury but not likely to cause death 2 = Behavior likely to result in death despite available medical care		Enter Code	Enter Code

The actual forms will be provided to the sites and should be used for assessment.

## **Appendix 13**

### **The Guidance for Blood Sampling**

**For patients aged 12 to 17 at the time of informed consent, blood sampling should be performed in accordance with the following EMA guidelines - Ethical considerations for Clinical Trials on Medicinal products conducted with the Paediatric population, 2008.**

As per the above guideline, the total blood loss per individual at any single time should not exceed 1% of the total blood volume, where total blood volume is estimated at 80 to 90 mL/kg body weight. In addition, total blood volume withdrawn over a period of four weeks should not exceed 3% of total blood volume, which estimates to 2.4 mL blood per kg of body weight.

#### **Blood sampling at each single visit**

Total blood volume taken at each single visit is recommended to be satisfied with the following criterion.

**Total blood volume at each single visit (mL)  $\leq$  Body weight (kg)  $\times$  0.8 (mL/kg)**

For example, if the body weight is 40 kg, the total amount of blood withdrawal at any single visit should not exceed 32 mL.

#### **Blood sampling for 4 weeks**

Total blood volume taken for 4 weeks is recommended to be satisfied with the following criterion.

**Total blood volume for 4 weeks (mL)  $\leq$  Body weight (kg)  $\times$  2.4 (mL/kg)**

For example, if the body weight is 40 kg, the total amount of blood withdrawal for 4 weeks should not exceed 96 mL.

If the total amount of blood withdrawal required is more than the permissible volume shown above, then the blood sample collection should be adjusted as per the following recommended order of priority accordingly in an ascending order of the number (i.e., "i" should be considered first).

## Appendix 13: The Guidance for Blood Sampling (cont.)

Maximum blood volume taken at any single visit is shown in Section 4.5.1.11 (the blood volumes for Hepatitis B viral DNA after baseline and CCSR project are included in the maximum blood volume summarized in Table 1).

### a. Screening

- i. Blood samples for local laboratory measurements (TB test and/or pregnancy test) should be collected on a different day to other blood samples at screening, and/or TB skin test is performed as per the local guidance.

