### **3.2.5 Rationale for Patient Population**

The limited literature on the topic of paediatric NMO suggests that the disease is diagnosed from around the age of 2 years upwards with a median age of onset of 14 years and a 3 or 4:1 female:male ratio. The spectrum of disease in children appears from the literature to be similar to that in adults with the possible exception of brain lesions and a relatively rapid progression of optic neuritis but the incidence is much lower at around 0.02/100,000 but varying by race (Jacob et al. 2012, Collongues et al. 2010, Lotze et al. 2008, Ketelslegers et al. 2012, Langer-Gould et al. 2011, Tillema 2012).

Recent population anthropometric data from the US, for example, show that the mean body weight for female aged 12 is 52.3 kg (5th to 95th percentile 30.6–75.7 kg) (Centers for Disease Control and Prevention). In the Japanese phase 1b RA study (SA-105JP), 4 of 11 patients treated with 120 mg satralizumab had a body weight under 45 kg. No difference in serum concentration of satralizumab between two groups by body weight (<45 kg and >45 kg) suggesting that it would be acceptable from a PK point of view to dose adolescents with the same 120 mg dose as adults.

The mean weight in older children and in boys is expected to be higher and therefore more similar to that in adults.

Animal toxicology studies with higher doses of satralizumab by body weight than are proposed here have shown no obviously drug-related toxicity. Adolescents aged 12 and upwards are expected to be developmentally mature in most ways.

There is precedent for the use of an anti-IL-6R monoclonal antibody (tocilizumab) to treat children, with and without concomitant immunosuppressant therapies (tocilizumab is licensed for the treatment of sJIA and pJIA internationally and also Castleman's disease in Japan). The safety profile in clinical trials and post-marketing has been generally similar to that in adults. Although these two antibodies are structurally different, the safety profile of tocilizumab can at least be taken to indicate the effect of IL-6R inhibition in the pediatric population.

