#### **4.1.1 Inclusion Criteria**

Patients must meet the following criteria for study entry:

1. Patients must be diagnosed as having either:
  - a. NMO as defined by 2006 criteria\*, or
  - b. NMOSD as defined by either of the following Wingerchuk 2007 criteria with anti-AQP4Ab seropositive status at screening‡.
    - i. Idiopathic single or recurrent events of longitudinally extensive myelitis (≥3 vertebral segment spinal cord MRI lesion)
    - ii. Optic neuritis: recurrent or simultaneous bilateral

For patients aged 12 to 17 years, a minimum of 4 patients should be positive for anti-AQP4Ab status at screening‡.

‡ Screening result is based on either the blood sample data collected at screening visit, or the blood sample data collected before the screening visit and measured by Sponsor's designee for analysis (see Section 4.5.1.5).

2. Clinical evidence of at least 2 documented relapses (including first attack) in the last 2 years prior to screening, at least one of which has occurred in the 12 months prior to screening.
3. EDSS score from 0 to 6.5 inclusive at screening.
4. Age 12 to 74 years, inclusive at the time of informed consent.
5. One of the following baseline treatments must be at stable dose as a monotherapy for 8 weeks prior to baseline\*\*.
  - a. Azathioprine.
  - b. Mycophenolate mofetil.
  - c. Oral corticosteroids.

\*\* For patients aged 12 to 17 years, either of the following baseline treatments for relapse prevention can be allowed:

- d. Azathioprine + oral corticosteroids.
  - e. Mycophenolate mofetil + oral corticosteroids.
6. Ability and willingness to provide written informed consent and to comply with the requirements of the protocol.

\*According to Wingerchuk et al. 2006, a diagnosis of NMO requires all of the following three criteria:

- I. Optic neuritis
- II. Acute myelitis
- III. At least two of three supportive criteria:
  - Contiguous spinal cord lesion identified on a magnetic resonance imaging (MRI) scan extending over 3 vertebral segments
  - Brain MRI not meeting diagnostic criteria for MS
  - NMO-IgG seropositive status

See Section 4.8 for the study criteria for adolescents who may be enrolled after the end of the double-blind period.

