**Table 1: Maximum Blood Volumes**

Visit(s)	Maximum blood volume taken (mL) 
Screening	28
Double-blind period	
Week 0	46
Week 2	34.5
Weeks 4 & 8	44
Weeks 5 & 6, Dose outside the visit window	3.5
Weeks 12, 24 & 48, every 24 weeks after Week 48 and at the withdrawal visit	47
Weeks 16, 20, 28, 32, 40, 44, every 4 weeks after Week 48	24.5 
Week 36	27.5
At extra visit on relapse	44
Follow-up assessment for adolescents	5.0
Extension period	
Weeks 0, 24, 48	32.5
Week 2	16
Weeks 4, 8, 16, 20, 28, 32, 40, 44	24.5
Every 12 weeks after Week 48	19
Weeks 12, 36 & Every 24 weeks after Week 48	27.5
Dose outside the visit window	3.5
At extra visit on relapse	29.5
Last observation visit and withdrawal visit	27.5
Follow-up assessment for adolescents	5.0

[1] The sample for CCSR project is included. The local laboratory samples (blood TB test and serum pregnancy test) are not included.

[2] 27.5 mL every 12 weeks after Week 48

Assessment of hsCRP, PK, IL-6, sIL-6R, ADA, anti-AQP4Ab (except screening), plasmablasts and complement (C3, C4, and CH50) will be performed in a blinded manner and results will not be available to site, PAREXEL and Sponsor until database lock for analysis of the double-blind period.

For patients aged 12 to 17 at the time of informed consent, please refer to [Appendix 13](#) for blood sample collecting (European Union, 2008).

For details on name and address of laboratory, sampling procedures, sample storage and shipment, see the materials in the Site Laboratory Binder.

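### Appendix 13's listed adjustments cannot bring the Table 1 maximum draws within its own 0.8 mL/kg single-visit limit for every eligible adolescent, at screening or at several later visits

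*Protocol*

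**What the plan says.** Protocol Table 1 (Section 4.5.1.11) lists maximum blood volumes by visit, with 28 mL at screening. Its first note adds: "The local laboratory samples (blood TB test and serum pregnancy test) are not included". Below the table, adolescents are sent to Appendix 13: "For patients aged 12 to 17 at the time of informed consent, please refer to".

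Appendix 13 starts from a principle, "the total blood loss per individual at any single time should not exceed 1% of the total blood volume", with total blood volume taken as 80 to 90 mL/kg. It turns this into a criterion of 0.8 mL per kg of body weight per visit, introduced as "Total blood volume taken at each single visit is recommended to be satisfied with the following criterion". Its worked example reads: "if the body weight is 40 kg, the total amount of blood withdrawal at any single visit should not exceed 32 mL". A second criterion of 2.4 mL/kg covers four weeks. If the required volume is higher, collection should be adjusted in a listed order:

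- Screening (list a): "Blood samples for local laboratory measurements (TB test and/or pregnancy test) should be collected on a different day to other blood samples at screening", and/or a TB skin test.
- From baseline (list b): drop the CCSR samples, use a urine pregnancy test, then drop anti-AQP4 antibody and/or plasmablast samples.

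On who may enter, inclusion criterion 4 (Section 4.1.1) is "Age 12 to 74 years, inclusive at the time of informed consent". Sections 4.1.1, 4.1.2 and 4.8 contain no weight criterion. Section 3.2.5 says of US anthropometric data: "the mean body weight for female aged 12 is 52.3 kg (5th to 95th percentile 30.6–75.7 kg". Section 4.5.1.1 and Table 6 first record body weight at baseline, after the screening draw.

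**The concern.** The adjustment lists exist so that a site can keep a small adolescent within the limit. At screening the only listed step moves or replaces blood that was never counted in the 28 mL, so the counted draw does not change. The counted screening tests (blood counts and transaminases, hepatitis serology, anti-AQP4 antibody) decide eligibility and are not on any list of samples to drop. After baseline the lists do remove counted blood, but not enough at visits that include hepatitis B DNA.

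What is at stake is a protection for minors that the protocol adopts for itself. A site that follows the appendix exactly for a low-weight adolescent can still end up above the stated limit, with no written next step. At screening it may also lack a scheduled weight from which to work out the limit.

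**Working it through.** **1. Reproduce the plan's figures.** Limit per visit = 0.8 × weight: 0.8 × 40 = 32 mL. Four-week limit = 2.4 × weight: 2.4 × 40 = 96 mL. Both match Appendix 13. The factors are 1% and 3% of 80 mL/kg.

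**2. Screening.** Threshold weight = 28 / 0.8 = 35.0 kg. The listed step leaves 28 mL unchanged, because the samples it affects are outside that figure. At 30.6 kg the limit is 0.8 × 30.6 = 24.48 mL, so 28 mL is 3.52 mL (14%) over. At 34 kg the limit is 27.2 mL and the excess is 0.8 mL.

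**3. What the post-baseline maxima contain.** Differences between Table 1 rows match the component volumes in Appendix 13:
- Week 0 minus Week 4: 46 − 44 = 2 mL (CCSR blood).
- Week 4 minus Week 2: 44 − 34.5 = 9.5 mL (CCSR serum and plasma).
- Week 12 minus Week 8: 47 − 44 = 3 mL (hepatitis B DNA).
- Week 36 minus Week 32: 27.5 − 24.5 = 3 mL (hepatitis B DNA).
- Extension Week 0 minus extension Week 12: 32.5 − 27.5 = 5 mL (anti-AQP4 antibody, European volume).

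Appendix 13 also states that hepatitis B DNA after baseline is included in Table 1.

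**4. Apply every listed reduction after baseline** (anti-AQP4 5 mL, plasmablasts 5 mL, CCSR as scheduled):
- Week 0: 46 − 2 − 9.5 − 5 − 5 = 24.5 mL.
- Week 2: 34.5 − 5 − 5 = 24.5 mL.
- Weeks 4 and 8: 44 − 9.5 − 5 − 5 = 24.5 mL.
- Weeks 16, 20, 28, 32, 40, 44: 24.5 mL as listed.
- Weeks 12, 24, 48: 47 − 9.5 − 5 − 5 = 27.5 mL.
- Week 36: 27.5 mL; Table 6 schedules none of the removable samples there.
- Extension Weeks 0, 24, 48: 32.5 − 5 = 27.5 mL.

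Thresholds: 24.5 / 0.8 = 30.6 kg and 27.5 / 0.8 = 34.4 kg.

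**5. Sensitivity of the screening threshold.** The protocol does not say what makes up the 28 mL. The alternatives below are assumptions:
- As listed: 28 mL, 35.0 kg.
- It contains the 5 mL European anti-AQP4 tube and the patient has the 3 mL Asian one: 26 mL, 32.5 kg.
- It contains 3 mL for hepatitis B DNA and the patient does not need that test: 25 mL, 31.25 kg.
- Both of these: 23 mL, 28.75 kg.
- It does not contain hepatitis B DNA and the patient needs it: 31 mL, 38.75 kg.

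**6. Four-week limit.** If screening falls within about two weeks of Week 0, the reduced volumes sum to 28 + 24.5 + 24.5 = 77 mL, and 77 / 2.4 = 32.1 kg. At the listed maxima the single-visit limit is therefore the tighter one for screening.

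**The case against.** Several points on the other side stand.

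- **The volumes are maxima.** Hepatitis B DNA is needed only for certain serology results. A patient who does not need it drops from 27.5 to 24.5 mL after baseline, and at screening could be as low as 23 mL (28.75 kg). The opposite case, 31 mL and 38.75 kg, is equally open on the text.
- **The limit is partly soft.** The criterion is introduced as a recommendation, and it takes the lower end of 80 to 90 mL/kg. At 0.9 mL/kg the thresholds would be 28 / 0.9 = 31.1 kg and 27.5 / 0.9 = 30.6 kg, close to the quoted 5th percentile. The written criterion nevertheless uses 0.8, and the principle and worked example are phrased as volumes that should not be exceeded.
- **Splitting the draw is possible.** Screening runs over 28 days and the limit applies per visit. Nothing forbids taking central-laboratory samples on separate days. A reader might infer that a site must either exceed the limit or omit eligibility tests; the documents do not support that. What they lack is a listed step: different-day sampling is offered only for local samples.
- **Few patients may be affected.** Section 1.3 says the double-blind period is complete. Sections 3.1.2 and 4.8 still allow adolescents to be recruited into the extension until at least 8 are enrolled, and the documents do not say whether that has closed.

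None of this makes the listed adjustments sufficient at the Table 1 maxima.

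**Conclusion.** The point holds as an internal inconsistency. At the Table 1 maxima and the written 0.8 mL/kg criterion, the listed adjustments meet the limit only from 35 kg at screening and from 34.4 kg at visits with hepatitis B DNA. Other main double-blind dosing visits come down to 24.5 mL, or 30.6 kg. The screening figure rests on the unstated composition of the 28 mL and ranges from 28.75 to 38.75 kg.

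Two further readings go too far. A reader might infer that screening is the only visit where the scheme fails; step 4 shows it also falls short at double-blind Weeks 12, 24, 36 and 48 and extension Weeks 0, 24 and 48, for patients who need the hepatitis B DNA tube. A reader might also infer a rate for adolescents generally from Section 3.2.5. By the definition of the percentile, at least 5% of the reference population of 12-year-old girls weigh under 35 kg. That is one sex at the youngest eligible age, and the same section expects boys and older children to be heavier.

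The matter concerns the safety and consistency of adolescent sampling. It does not touch power or the primary analysis.

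**What to change.** Reconcile Table 1, both Appendix 13 lists (screening and from baseline) and the age-only entry rule, so that the listed adjustments bring every eligible weight within the stated limits. State whether the 28 mL includes hepatitis B DNA and which anti-AQP4 tube volume it assumes. Make body weight available before the screening draw. How the passages are reconciled is for the sponsor and clinical team; no volume or sampling rule is proposed here.

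The cost is wording in Table 1 and Appendix 13 and one weight measurement at screening. Depending on the solution chosen, a few low-weight adolescents might need an additional sampling day.
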